#### 8.4 Intervention

## 8.4.1 Dosage and administration

Both nivolumab and ipilimumab will be stored, mixed and administered as per published commercial guidelines (please see Appendix 1). For participants in the combination arm, nivolumab will first be administered intravenously at a dose of 1 mg/kg of body weight over a period of approximately 60 minutes, once every 3 weeks for 4 doses. Approximately 30 minutes after the completion of each nivolumab infusion, participants will receive 3 mg/kg of ipilimumab over a period of approximately 30 minutes.

In the ipilimumab monotherapy group, participants will receive 3 mg/kg of ipilimumab over a period of approximately 30 minutes once every 3 weeks for 4 doses.

## 8.4.2 Monitoring and Dose Delay Criteria

Participants should be assessed for toxicity prior to each dose; dosing will occur only if the clinical assessment and laboratory test values are acceptable. If toxicity occurs as indicated below, participants in both study arms should have study drug(s) held. In participants who are in the combined treatment arm, both drugs should be held for any toxicity. Dose delays are designed to maximize treatment for those who derive clinical benefit from treatment while ensuring participant safety. Participants should follow timed assessments, and continuation on study is at the PI's discretion.

Nivolumab and/or ipilimumab administration should be delayed for the following reasons:

- Grade ≥2 non-skin, drug-related AEs with the following exceptions:
  - Grade 2 drug-related fatigue or laboratory abnormalities do not require a treatment delay
- Any Grade 3 skin, drug-related AE
- Any Grade 3 drug-related laboratory abnormalities with the following exceptions for lymphopenia, leukopenia, AST, ALT or total bilirubin
  - o Grade 3 lymphopenia or leukopenia does not require dose delay
  - o If a participant has a baseline AST, ALT or total bilirubin that is within normal limits, delay dosing for drug-related Grade ≥2 toxicity
  - If a participant has a baseline AST, ALT or total bilirubin that is within the Grade 1 toxicity range, delay dosing for drug-related Grade ≥3 toxicity
- Any AE, laboratory abnormalities, or intercurrent illness, which in the judgment of the Investigator warrants delaying the dose of study drug.

#### 8.4.3 Management Algorithms for Immune-related Adverse Events

Immuno-oncology agents are associated with AEs that can differ in severity and duration from AEs caused by other therapeutic classes. Early recognition and management of AEs associated with immuno-oncology agents may mitigate severe toxicity. Immune-related AEs will be managed as per published guidelines. Please see Appendix 2 for further details.

# 8.4.4 Dose Modifications

Nivolumab and ipilimumab dose reductions and escalations are not permitted in either study arm.

#### **8.4.5** Criteria to Resume Treatment

Criteria to resume treatment apply for all drug-related AEs attributed to nivolumab, ipilimumab or both. Participants may resume treatment with study drug(s) when the drug-related AEs resolve to Grade ≤1 or baseline value with the following exceptions:

- Participants may resume treatment in the presence of Grade 2 fatigue
- Participants who have not experienced a Grade 3 drug-related skin AE may resume treatment in the presence of Grade 2 skin toxicity
- Drug-related endocrinopathies adequately controlled with only physiologic hormone replacement may resume treatment
- See Appendix 2 for detailed management algorithms of irAEs

## 8.5 Blinding

Not Applicable.

## 8.6 Treatment Accountability and Compliance

Administration of study drugs will be supervised by study personnel or assigned infusion room nursing staff, who will monitor compliance. Study drugs accountability will be maintained in the Pharmacy Source documents i.e. accountability logs or in the study master file, as required.

## 9 STUDY PROCEDURES

Table 3 outlines the timing of procedures, and assessments to be performed throughout the study. See Sections 9.1 to 9.2.3 for additional details of study procedures.

**Table 3: Schedule of Assessments** 

	Baseline/ Screening a	Cycle 1 b	Cycle 2	Cycle 3	Cycle 4	Follow-up Visit 1 and 2 d	Additional Follow-up Visits e	Early Termination Visit f
Obtain Informed Consent	X							
Participant History	X							
Inclusion/Exclusion criteria	X							
Biopsy of Target Lesion c	X	X						
Prior/concomitant medications	Collected from Screening to Follow-up							
Physical Examination	X	X	X	X	X	X		X
Performance status	X	X	X	X	X	X		X
Height/Weight	X	X	X	X	X	X		X
Vital Signs	X	X	X	X	X	X		X
Complete Blood Count	X	X	X	X	X	X		X
Complete Metabolic Panel, LDH	X	X	X	X	X	X		X
Thyroid function testing g	X	X	X	X	X	X		X
Pregnancy test (serum)	X	X	X	X	X	X		X
HCV, HBV, HIV Testing	X							
CT scan h	X				X	X		X
MRI Brain	X							
ECG	X							
Adverse Events	Collected from consent to 100 days after drug discontinuation							
Drug Administration		X	X	X	X			
Research blood (~40mL)	X	X	X	X	X	X		X

PD-L1 expression on banked tumor specimen if available	X					
Survival Data				X	X	X

<sup>aScreening assessments are recommended to be performed within 28 days prior to treatment unless otherwise specified above

<sup>bEach cycle=21 days±4 days

<sup>cBiopsy at baseline for all participants within 14 days of Cycle 1, Day 1. On-treatment biopsy must be performed within 14 days±5 days of first dose of study drug.

<sup>dFollow up period begins when the last dose of study therapy is administered. Follow-up visit 1=21 days from last dose  $\pm$  7 days. Follow-up visit 2=42 days from last dose  $\pm$  7 days. If the participant completed follow-up visit 1 and follow-up visit 2 and *has* progressed, the participant is not required to have scans every 12 weeks. Survival could be assessed via calls every 3 months ( $\pm$ 7 days). If a participant is off treatment and *has not* progressed, they would continue to visit the site and have scans every 12 weeks.

 $^{\rm e}$ Additional follow-up visits will be scheduled every 3 months  $\pm 7$  days. For participants who end treatment for toxicity, scans should continue every 12 weeks until progression of disease. After progression of disease, survival calls will occur every 3 months ( $\pm 7$  days).

<sup>fFor participants who terminate the study early, follow-up will begin 21 days from the last dose (follow-up visit 1).

<sup>gTSH will be checked at every visit and will reflex to check free T4 if abnormal.

<sup>hPer standard of care to provide data for RECIST measurements as appropriate for each participant per the investigator physician. CT scans will be performed at baseline (-7 days), Week 12, Week 18, and every 12 weeks (±7 days) thereafter until progression of disease, death, or end of study for up to 2 years. A CT scan of the chest, abdomen and pelvis or an MRI of the abdomen and pelvis plus a non-contrast CT of the chest are acceptable.

# 9.1 Participant Informed Consent

Prior to performing any study-related procedures, the Investigator (or his/her designated staff member) will obtain written informed consent from the participant. After informed consent is obtained, the participant will be registered on study and begin "Screening/Baseline" evaluation. They will be monitored for AEs and clinical progression. They will continue to be followed periodically utilizing phone, email, fax, or postal mail for OS data for up to 2 years.

# 9.2 Procedures by Study Visit or Period

#### 9.2.1 Pretreatment Evaluation

The following procedures and assessments must be performed prior to treatment start. All intervals are defined with respect to Cycle 1, Day 1 of treatment.

- 9.2.1.1 At any time prior to the start of the study drug
  - Histologic confirmation of melanoma by the institution's pathologist.
- 9.2.1.2 Within 4 weeks prior to the start of the study drug
  - Written Informed Consent
  - A contrast-enhanced CT or magnetic resonance imaging (MRI) of the brain as well as of the chest, abdomen and pelvis. A CT scan of the chest, abdomen and pelvis or an MRI of the abdomen and pelvis plus a non-contrast CT of the chest are acceptable.
  - Electrocardiogram (ECG)

## 9.2.2 Within 2 Weeks Prior to the Start of the Study

- Updated medical history and physical examination including measurement of vital signs and ECOG performance status
- Medication review
- Complete blood count, comprehensive metabolic panel, thyroid stimulating hormone (TSH) and free T4
- HIV enzyme-linked immunosorbent assay, HBV Core antibody, HBV surface antigen, HCV antibody. HIV consent will be obtained and documented as per the institution's guidelines.
- Serum beta-human chorionic gonadotropin for women of child-bearing potential (defined as women less than 55 years of age)
- Fresh core biopsy of target lesion that obtains a goal of 4 adequate cores, with 2-3 considered acceptable or excisional biopsy.

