#### 7.1 Inclusion Criteria

All participants must meet all of the following criteria at screening and baseline to participate in the study:

- 1. AJCC (2009) Stage IV cutaneous melanoma or Stage III cutaneous, acral or mucosal melanoma that is judged inoperable. Participants with a history of uveal melanoma are not eligible.
- 2. Measurable disease, defined as at least one lesion that can be accurately measured in at least one dimension (longest diameter to be recorded) as >20 mm with conventional techniques or as >10 mm with computerized tomography (CT) scan. Participants must have at least one measurable lesion by RECIST and a separate lesion amenable to biopsy.
- 3. Histologic proof of melanoma reviewed and confirmed by the enrolling site.
- 4. Previous treatment with a PD-1 or PD-L1 inhibitor with documented progression of disease on most recent CT scan. Progression of disease is defined as 1) the appearance of a new measurable lesion (>10 mm) on cross-sectional imaging or physical examination OR 2) enlargement of previously detected lesions on two consecutive imaging studies OR 3) enlargement of a previously detected lesion with correlative symptomatology on one cross-sectional imaging study. Participants remain eligible if they had a previous response to a PD-1 inhibitor, including participants who had a complete response, PR or SD. Any participant who had refractory or relapsed disease is eligible for study enrollment. Treatment populations are defined in Section 12.
- 5. Participants who received adjuvant PD-1 therapy who then develop measurable disease are eligible. However, they must have received their last dose of PD-1/PD-L1 blockade within two months of enrollment in this study. They will be stratified with participants who have primary progressive disease.
- 6. Life expectancy of greater than 3 months.
- 7. Age  $\geq$  18 years old.
- 8. ECOG performance status = 0 or 1 or Karnofsky Performance Status equivalent
- 9. Participants must have adequate organ and marrow function as defined below:
  - a. White blood cells (WBC) >2, 000/mcL
  - b. Absolute neutrophil count >1,500/mcL
  - c. Platelets >100,000/mcL

- d. Hemoglobin > 9.0 g/dL
- e. Total bilirubin  $\leq 1.5$  X institution's upper limit of normal

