#### Arm A:

- Participants will be required to start treatment within 14 days of their pre-treatment biopsy. The pre-treatment biopsy is considered standard of care.
- One dose of ipilimumab and nivolumab administered together constitutes one cycle; they will be administered in the manner described in Section 8.4.
- Cycles will be administered every 21 days±4 days for up to 4 cycles.

- CT scans will be administered at weeks 12 and 18 and every 12 weeks for up to 2 years after study treatment begins. These are considered standard of care.
- Blood will be drawn at every cycle during treatment and during follow-up visits. Standard bloodwork, such as complete blood count (CBC) and comprehensive metabolic panel (CMP), are part of routine care. Other bloodwork (approximately 40 mL) will be drawn which is solely for the purpose of research.
- An on-treatment biopsy will be required within 14 days ± 5 days of the start of Cycle 1. This is solely for the purpose of research. All reasonable efforts will be made to biopsy the same lesion pre- and on-treatment.

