## 10.1.2 Target" and "Non-Target" lesions

# 10.1.2.1 Target Lesions

All measurable lesions up to a maximum of 5 lesions representative of all involved organs should be identified as target lesions and recorded and measured at baseline. Target lesions should be selected on the basis of their size (lesions with the longest dimension) and their suitability for accurate repetitive measurements.

A sum of the longest dimension (LD) for all target lesions will be calculated and reported as the baseline sum LD. The baseline sum LD will be used as reference to further characterize the objective tumor response of the measurable dimension of the disease.

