### **Tumor tissue specimens**

Pre- and on- treatment tumor specimens will be obtained on all eligible participants. Tumor specimens collected may include (1) 4 core biopsy specimens or (2) an excision biopsy or (3) a specimen from surgical resection of a tumor. In the case of the core biopsy specimens, 3 core biopsies will be snap frozen and 1 biopsy will be formalin fixed and preserved in paraffin embedded blocks (FFPE). In the case of excisional or surgical specimens, approximately ½ of the specimen will be snap frozen and the other ½ will be formalin fixed and paraffin embedded.

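### The protocol contradicts itself on whether the biopsied lesion is a RECIST target lesion, and no rule says how an excised target lesion is scored for response

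*Protocol*

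**What the plan says.** Five parts of the plan decide which lesion is sampled and whether it is also measured for response.

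- **Eligibility.** Protocol 7.1, inclusion criterion 2: "Participants must have at least one measurable lesion by RECIST and a separate lesion amenable to biopsy".
- **Biopsy instruction.** Protocol 9.2.2, before treatment: "Fresh core biopsy of target lesion that obtains a goal of 4 adequate cores, with 2-3 considered acceptable or excisional biopsy". The row in Protocol Table 3, repeated in SAP 8.2, reads "Biopsy of Target Lesion" and is marked at Baseline/Screening and at Cycle 1. Its footnote adds: "On-treatment biopsy must be performed within 14 days±5 days of first dose of study drug".
- **Specimen type.** Protocol Appendix 3, covering both time points: "Tumor specimens collected may include (1) 4 core biopsy specimens or (2) an excision biopsy", with surgical resection as a third option. Section 8 says for each arm: "All reasonable efforts will be made to biopsy the same lesion pre- and on-treatment".
- **Target selection.** Protocol 10.1.2.1: "All measurable lesions up to a maximum of 5 lesions representative of all involved organs should be identified as target lesions". It goes on to ask that selection take account of size and of how well a lesion can be measured repeatedly. It does not mention biopsied lesions, and no section says how an excised target lesion is scored.
- **Response window.** SAP 5.4.1 closes the best-response window at subsequent anticancer therapy, which includes tumor-directed surgery. It does not say whether a study biopsy counts as such surgery. SAP 5.4.4 plans no sensitivity analyses.

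**The concern.** Section 9.2.2 and the two schedules use a term that section 10 reserves for the lesions whose longest dimensions form the baseline sum. Criterion 2 points to a different lesion, but it does not settle the matter. It requires that a separate lesion exist for biopsy, not that this lesion be kept out of the sum. In a participant with five or fewer measurable lesions, a biopsy lesion that is itself measurable falls under 10.1.2.1 unless the investigator chooses to leave it out.

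If such a lesion is cut out after the baseline scan, the sum falls without any drug effect. What is at stake is the primary endpoint: an investigator-assessed response rate by Week 18, open-label, in 12 participants per arm, set beside a historical 10.9%. The opposite error is also possible, because the SAP's surgery cut-off can be read to remove a participant's response window altogether.

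**Working it through.** The plan gives no figure for this mechanism. As a check on the setting, the exact 95% interval for 4/12 in SAP Table 1, (9.9%, 65.1%), reproduces with the Clopper-Pearson formula.

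**1. Can a target lesion be removed after the baseline sum is fixed?** Baseline imaging may be up to 28 days before therapy (Protocol 9.2.1.2 and 10.1.3), or within 7 days (Table 3, footnote h). The pre-treatment biopsy falls within 14 days of Cycle 1 Day 1, and section 8 places it after eligibility, including measurable disease, is confirmed. Even under the 7-day window, a scan on day -6 and a biopsy on day -3 is allowed. The on-treatment biopsy, at 14 ± 5 days (days 9 to 19), always follows baseline imaging.

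**2. How far does the sum fall?** If the removed lesion held a share *s* of the baseline sum, the fall is *s*, and the 30% threshold for partial response (10.1.5) is met when *s* ≥ 0.30. With *k* equal lesions, *s* = 1/*k*. The remaining lesions may grow by a fraction *g* and the sum still be 30% below baseline if (*k* − 1)(1 + *g*)/*k* ≤ 0.70, that is *g* ≤ 0.70*k*/(*k* − 1) − 1.

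| Equal target lesions | Fall from removing one | Meets 30% alone | Growth allowed in the rest |
|---|---|---|---|
| 2 | 50% | yes | 40% |
| 3 | 33.3% | yes | 5% |
| 4 | 25% | no | none (rest must shrink 6.7%) |
| 5 | 20% | no | none (rest must shrink 12.5%) |

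A sole target lesion that was excised would give a 100% fall. The growth column compares with baseline only. A rise of 20% and at least 5 mm between two scans would be progression under 10.1.5.

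**3. Would it be confirmed?** Response needs two assessments at least 4 weeks apart. The Week 12 and Week 18 scans are 6 weeks apart, and an excision is permanent, so both show the fall. New lesions or unequivocal non-target progression would prevent a partial response.

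**4. Core biopsy.** A single 20 mm target would have to lose 0.30 × 20 = 6 mm of longest dimension. Nothing in the documents suggests that cores do this.

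**5. Effect on the response rate.** One non-responder scored as a responder adds 1/12 = 8.3 points, for example from 3/12 (25.0%) to 4/12 (33.3%). Protocol 12.1 calls an arm promising at 4 or more of 12. With *m* artefactual responders (an assumed number) and a true rate of 10% in the others, the chance of reaching 4 is P(Bin(12 − *m*, 0.10) ≥ 4 − *m*):

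- *m* = 0: 0.0256
- *m* = 1: 0.0896
- *m* = 2: 0.264

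The SAP disclaims hypothesis testing, so these probabilities only illustrate sensitivity.

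**6. The other reading of the SAP.** If an on-treatment excision counts as tumor-directed surgery, the best-response window closes between days 9 and 19, well before the Week 12 scan (12 × 7 = day 84). With no scheduled post-baseline assessment inside the window, the participant is a non-responder. A true responder handled this way costs the arm 8.3 points. A pre-treatment excision precedes randomization, where the window opens, so the cut-off does not reach it.

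**The case against.** There is a serious case that this is mostly a matter of wording.

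- **The term may mean the lesion aimed at for biopsy.** Section 8 speaks only of an unresectable or metastatic lesion, and section 7 allows no exceptions to eligibility. This is a fair reading, but the text would still need correcting, and 10.1.2.1 would still admit the biopsied lesion.
- **Section 10.1.2.1 asks for lesions that can be measured repeatedly.** That gives an investigator a reason to leave out a lesion due for excision. It is a judgement rather than a rule, and it may come before anyone has decided to excise.
- **Core biopsy is the main route.** It is listed first, and a fully excised lesion cannot be sampled again, which sits badly with the effort to biopsy the same lesion twice. This makes a pre-treatment excision less likely. It does not rule out cores at baseline and excision of the same lesion on treatment.
- **Other limits exist.** Exclusion criterion 2 bars major surgery in the 14 days before study drug, so some pre-treatment resections are blocked. A baseline scan taken after the biopsy would already omit the excised tissue. A biopsy lesion that is not measurable never enters the sum. Participants enrol with documented progression, so growth or new lesions will often defeat an artefactual response.

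These points reduce how often the problem could arise. None of them closes it.

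A reader might infer that the protocol clearly orders target-lesion biopsy, and that any biopsy, core included, can create a response. The documents do not support that: the instructions conflict, and the arithmetic works only for excision or resection.

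**Conclusion.** The point stands in conditional form. The plan is inconsistent about which lesion is biopsied, permits excision at both time points, and has no rule keeping the lesion out of the sum or scoring its loss. A false confirmed partial response requires that the excised lesion was a target, that it was removed after the baseline scan, that it held at least 30% of the baseline sum, and that nothing else offset the fall. The *k*-lesion figures assume equal sizes; the 30% share does not.

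The 8.3 points are a per-event figure. The documents give no frequency of excision or of biopsied target lesions, so they do not support a statement that the reported response rate will be inflated, or by how much. The direction is also open, since the SAP's surgery cut-off could turn the same event into a non-response. With 12 participants per arm, even one case is large enough to justify settling the rule in advance.

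**What to change.** 1. **Protocol 9.2.2, Protocol Table 3 and SAP 8.2:** reconcile the biopsy wording with inclusion criterion 2.
2. **Protocol 10.1.2.1:** add that the lesion chosen for biopsy is not selected as a target lesion.
3. **SAP 5.4.1:** state that loss of a lesion through study excision does not count toward complete or partial response, and that a study biopsy is not tumor-directed surgery for the best-response cut-off.
4. **If target lesions are already selected:** report the response rate with biopsied lesions left out of both the baseline and the follow-up sums, and say beforehand how a participant left with no target lesion is counted. This replaces the statement in SAP 5.4.4 that no sensitivity analyses are planned. It must be in place before database lock, because SAP section 2 allows no changes from then on.

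The cost is a formal amendment (Protocol 13.8.1 requires one for any change), a short SAP revision, and one fewer target lesion in some participants. Eligibility is unchanged, because criterion 2 already requires a separate lesion.

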#### 9.2.3 Unscheduled Visits

The Investigator may at his/her discretion arrange for a participant to have an unscheduled assessment, especially in the case of AEs that require follow-up or an AE considered by the Investigator to be possibly related to the use of study drug. The unscheduled visit page in the eCRF must be completed.

#### 10 EFFICACY ASSESSMENTS

## 10.1 Response in Solid Tumor Criteria 1.1

#### 10.1.1 Definitions of Measurable Disease

Measurable disease is defined as at least 1 target lesion, i.e. one that can be accurately measured in at least 1 dimension (longest dimension to be recorded). Each lesion must be 10 mm in 1 short axis as measured on CT or MRI; lymph nodes must be at least 15 mm in short axis.

## 10.1.2 Target" and "Non-Target" lesions

# 10.1.2.1 Target Lesions

All measurable lesions up to a maximum of 5 lesions representative of all involved organs should be identified as target lesions and recorded and measured at baseline. Target lesions should be selected on the basis of their size (lesions with the longest dimension) and their suitability for accurate repetitive measurements.

A sum of the longest dimension (LD) for all target lesions will be calculated and reported as the baseline sum LD. The baseline sum LD will be used as reference to further characterize the objective tumor response of the measurable dimension of the disease.

